COPANLISIB TREATMENT SUBPROTOCOL CO- [name], PhD
CHAIR:

Version Date: July 16, 2021

NOTE: This subprotocol (EAY131-Z1G) should
be used in conjunction with the
MATCH Master Protocol (EAY131).

SUBPROTOCOL ACTIVATION DATE

Incorporated in Addendum #13
Addendum #16
Addendum #22
Addendum #25
Addendum #29

Agent	IND#	NSC#	Supply
COPANLISIB	IND Sponsor: DCTD, NCI IND#:	784727	NCI Supplied

Table of Contents

Molecular Analysis for Therapy Choice (MATCH)	i
MATCH Treatment Subprotocol Z1G: Phase II Study of Copanlisib in Patients with Tumors with PTEN Loss by IHC and any PTEN Sequencing Result	1
Table of Contents	2
Schema	4
1. Introduction	5
1.1 PI3K/AKT/mTOR Pathway in Cancer	5
1.2 Copanlisib	5
1.3 Safety	8
1.4 Efficacy	9
2. Selection of Patients	11
2.1 Eligibility Criteria	11
3. Copanlisib Treatment Plan	14
3.1 Dosage and Administration Schedule	14
3.2 General Concomitant Medication and Supportive Care Guidelines	15
3.3 Adverse Event Reporting Requirements	16
3.4 Comprehensive Adverse Events and Potential Risks List (CAEPR) for Copanlisib dihydrochloride (BAY 80-6946 dihydrochloride, NSC 784727) 19	19
3.5 Dose Modifications	22
3.6 Supportive Care	28
3.7 Duration of Agent-specific treatment	28
3.8 Duration of Follow-Up	28
4. Study Parameters	29
4.1 Therapeutic Parameters for CopanlisibTreatment	29
5. Drug Formulation and Procurement	31
5.1 Copanlisib (NSC #784727)	32
6. Translational Studies	34
7. References	34
Appendix I Actionable Mutation for Sub-Protocol EAY131-Z1G is PTEN Loss on IHC	36
Appendix II Patient Clinical Trial Wallet Card	44
Appendix III Management of Transient Glucose Increase On the Day of Copanlisib Infusion	45
Appendix IV Dose Modification of Copanlisib for Arterial Hypertension	46

Rev. Add29

TREATMENT SUBPROTOCOL CHAIR

[figure not shown]
[name], PhD
The University of Texas
MD Anderson Cancer Center
The Department of Investigational Cancer
Therapeutics
[name]
[contact]
Email: [contact]

TREATMENT SUBPROTOCOL CO-CHAIR

Rev. Add29

[name], PhD
MD Anderson Cancer Center
Department of Melanoma Medical Oncology
[name]
[name]
[contact]
[contact]
E-mail: [contact]

Schema

Cycle = 28 days
Accrual Goal: 35

1. Introduction

1.1 PI3K/AKT/mTOR Pathway in Cancer

The PI3K/AKT/mTOR signaling pathway is one of the most frequently activated signaling cascades in cancer.^{1,2} Class I PI3K is activated by a variety of signals, including many receptor tyrosine kinases (RTKs), cell-cell contacts, and activated RAS proteins, among others.³ The activated PI3K phosphorylates phosphatidylinositols in the cell membrane at the 3'-OH position. These phospholipids interact with proteins that contain a pleckstrin homology (PH) domain, including the serine-threonine kinase AKT, also known as protein kinase B (PKB). Interactions of PH domain-containing proteins cause them to co-localize at the cell surface, where they often interact and activate each other (i.e. activation of AKT by phosphorylation of PDK1). The activated AKT acts on multiple effectors to regulate a number of key cellular functions, including angiogenesis, proliferation, survival, motility, and metabolism. PTEN, a lipid phosphatase that dephosphorylates phosphatidylinositols at the 3'OH position, is a critical negative regulator of PI3K activity.

The PI3K/AKT/mTOR signaling pathway is activated by many oncogenic events.^{4,5} The PI3K/AKT/mTOR pathway is a key effector of activating oncogenic events that occur upstream of the pathway, including activating hotspot mutations (i.e EGFR) and gene amplifications (i.e. HER2/neu) affecting RTKs, and hotspot mutations in RAS family proteins (i.e. Kras). The pathway may also be activated by hotspot mutations in components of the pathway, including PIK3CA, AKT1, and AKT3. Signaling through the PI3K/AKT/mTOR signaling pathway can also be activated by loss of function of PTEN. Previous studies support that loss of PTEN function most commonly results from somatic mutations and gene deletions that cause loss of PTEN protein expression, with >95% loss of PTEN protein expression correlating with increased activation of AKT and other pathway effectors.⁶⁻⁸ PTEN function can also be disrupted by mutations that disrupt the phosphatase domain of the PTEN protein, thus causing a loss of catalytic function.⁹⁻¹¹

The high frequency of activation of the PI3K/AKT/mTOR signaling pathway in cancer makes it an attractive target for therapeutic development. In particular, there is a strong rationale to test the hypothesis that agents that inhibit the pathway will achieve clinical benefit in patients with alterations in the pathway itself, particularly PIK3CA mutations and PTEN loss.¹² However, preclinical data suggest that different oncogenic events in this pathway (i.e. PIK3CA mutations and PTEN loss) may have different functional consequences, a hypothesis that is further supported by the frequently observed overlap of mutations of this pathway in tumors.¹²⁻¹⁴ Thus, this protocol is designed to specifically test the hypothesis that complete loss of PTEN protein expression will predict clinical benefit from treatment with the pan-PI3K inhibitor copanlisib in patients without PIK3CA mutations.

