
1.4 Efficacy

The data so far from copanlisib trials in lymphoma imply that low or total loss of PTEN expression predicts for response. Expansion of study 12871 in lymphomas showed 6 PRs and 1 CR among 9 patients treated. Four of six patients with null or low (< 5%) PTEN expression by IHC had a response (66%) whereas only 15% of patients with higher PTEN expression by IHC responded (Bayer data). There is not as much data available for solid tumors, but the latest data is from the expansion of study 12871 in 25 solid tumors. One patient with

endometrial cancer had a complete response, and she had PTEN loss by IHC, as well as PTEN and PIK3CA mutations. Two patients with extended stable disease also had PTEN loss by IHC. Due to the small number of patients with solid tumors entered, and the very few responses in these patients, we have very little data on the relationship of PTEN loss to response rate with this agent. However, the data that do exist conform to our level of evidence 3: at least one patient with PTEN loss by IHC responded to copanlisib with solid tumors (and several did so with lymphomas).

Out of 46 patients in study 16790 clinical benefit rate (CR, PR or SD) was seen in 38% of patients with solid tumors. Interestingly, all 6 patients with follicular lymphoma experienced an objective response. One patient is still on treatment for over 3 years now. On exploratory analysis of the lymphoma patients, one patient had complete PTEN loss and four patients had low PTEN (1-5 % staining of tumor cells).

Based on this a phase 2 study, 16349 was undertaken. 29 out of 32 patients with indolent lymphoma had a clinical benefit rate with an objective response rate of 44%. Among patients with aggressive lymphomas, 20 out of 46 patients had a clinical benefit with an objective response rate of 26%. Analysis of PTEN and mutations in study 12871 showed about 50% of solid tumors had complete loss of PTEN by IHC. Copanlisib is being tested in combination with chemotherapy in studies 12874, 12875 and 12876 and 2 patients in study 12875 with complete loss of PTEN achieved partial response or prolonged disease stabilization. Multiple phase 2 and 3 studies have been launched in Non-Hodgkin's lymphoma but none of the studies require tumors to have PI3K mutations or PTEN loss by IHC. Based on our data the anticipated response rate should be around 20% (Janku et al. Cell Rep 2014).

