Complete loss of PTEN by IHC is rarer than mutation in PTEN. We have already accrued an arm that had complete loss of expression of PTEN by IHC in a time period of less than one year. We have quite a few PTEN losses that have been screened while arm P has been closed, and these patients, if their biopsy occurred < 5 months previously, would be offered participation in this arm. MATCH is now in the "rare variant initiative" and is not screening biopsies currently. Rather, patients can enter MATCH with results from an outside assay. If a patient has a PTEN mutation, their archived specimen will be assayed by IHC for PTEN expression in order to be able to assign them to arm Z1G or Z1H, along with the results of the outside assay.

This arm has some overlap with Arm Z1F, which will allow patients with PTEN loss to enroll, but Z1G and Z1H do not allow patients with PIK3CA mutation. If patients have both a PIK3CA mutation and PTEN IHC loss, patients will be assigned to Z1F. Arms Z1F, Z1H, and Z1G will provide complementary information as there are very likely to be patients in Z1F with PIK3CA mutation but PTEN intact; PIK3CA mutation with loss of PTEN expression and PIK3CA mutation with PTEN mutations but retained expression of PTEN by IHC (the latter two conditions occur in half or less of patients, depending on tumor types enrolled). However, the arms Z1H and Z1G will only have patients with PTEN loss or mutation. We will thus get a signal as to whether the agent is active when there are coexisting abnormalities in PTEN and PIK3CA, PIK3CA abnormalities alone, or PTEN abnormalities alone (as well as if expression of PTEN is null).

2. Selection of Patients

Each of the criteria in the checklist that follows must be met, along with the eligibility in the MATCH Master Protocol, in order for a patient to be considered eligible for this study. Use the checklist to confirm a patient's eligibility. For each patient, this checklist must be photocopied, completed and maintained in the patient's chart.

In calculating days of tests and measurements, the day a test or measurement is done is considered Day 0. Therefore, if a test is done on a Monday, the Monday four weeks later would be considered Day 28.

ECOG-ACRIN Patient No. _____

Patient's Initials (L, F, M) _____

Physician Signature and Date _____

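### Do the evidence for arm Z1G and its anticipated 20% response rate rest on a kind of patient that the arm excludes?

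*Protocol*

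**What the plan says.** Section 1.1 frames the hypothesis as "complete loss of PTEN protein expression will predict clinical benefit from treatment with the pan-PI3K inhibitor copanlisib in patients without PIK3CA mutations". Criterion 2.1.2 requires complete PTEN loss by immunohistochemistry (IHC), and 2.1.3 excludes PIK3CA and other pathway aberrations. Section 1.4 gives the assignment rule for overlapping cases: "If patients have both a PIK3CA mutation and PTEN IHC loss, patients will be assigned to Z1F".

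The supporting evidence is in Section 1.4. Among 25 solid tumours in the expansion of study 12871, one patient with endometrial cancer had a complete response, and "she had PTEN loss by IHC, as well as PTEN and PIK3CA mutations". The section concedes that "we have very little data on the relationship of PTEN loss to response rate with this agent", then holds that its level of evidence 3 is met because "at least one patient with PTEN loss by IHC responded to copanlisib with solid tumors". It also reports, for study 12871, that "about 50% of solid tumors had complete loss of PTEN by IHC", and, for study 16790, that "all 6 patients with follicular lymphoma experienced an objective response". It closes with "Based on our data the anticipated response rate should be around 20" per cent, citing a report on PIK3CA and PTEN in early-phase trials of PI3K/AKT/mTOR inhibitors (reference 12). The Schema gives an accrual goal of 35.

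**The concern.** Section 1.1 separates PTEN loss from PIK3CA mutation because the two may act differently. It is therefore odd that the one solid-tumour responder offered as evidence carried both. She meets the wording used for level 3, but she belongs to the population that Z1G sends elsewhere.

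The 20% adds to the unease. It follows an admission of very little data for this agent, and no numerator, denominator, agent or genotype is given. The title of the cited report covers two genes and a whole drug class. If 20% were the design alternative behind 35 patients, and the true rate in eligible patients were much lower, the arm could be underpowered or a low count misread.

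There is also a point of wording. Every Z1G patient has PTEN loss, so the arm alone can estimate activity but cannot show that PTEN loss predicts it.

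**Working it through.** **Can 20% be reproduced?** No. No count in the Protocol yields it for eligible patients. It is attributed to an outside report that is not at hand, so it can be neither confirmed nor refuted here.

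**Does other evidence in Section 1.4 fit Z1G?**
- Two further PTEN-loss solid tumours had extended stable disease, not response. Their PIK3CA status is not given.
- Two PTEN-loss patients in study 12875 had a partial response or prolonged stabilisation, but with chemotherapy. Their PIK3CA status is not given.
- The 38% in study 16790 combines complete response, partial response and stable disease.
- The six follicular lymphoma responders would be barred as indolent lymphoma (2.1.12). Of five lymphoma patients listed with complete loss or low PTEN, four were low rather than completely lost.
- The lymphoma figure of 4 responders in 6 pools null with low expression.

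So one solid-tumour response on copanlisib alone is described, and none is shown to fit Z1G. That partly reflects unreported PIK3CA status rather than demonstrated ineligibility.

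**What do the counts say about 20%?** Intervals are exact (Clopper-Pearson, 95%). With zero responses in n, the upper limit is 1 − 0.025^(1/n).

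| Set | Count | Rate | 95% interval |
|---|---|---|---|
| All 25 solid tumours | 1/25 | 4.0% | 0.1% to 20.4% |
| PTEN loss, if half of 25 | 1/12 | 8.3% | 0.2% to 38.5% |
| PTEN loss, if half of 25 | 1/13 | 7.7% | 0.2% to 36.0% |
| PTEN loss, responder removed | 0/11 | 0% | up to 28.5% |
| PTEN loss, responder removed | 0/12 | 0% | up to 26.5% |
| All solid tumours, responder removed | 0/24 | 0% | up to 14.2% |

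The last row falls below 20%, but on the same assumption about half of those tumours kept PTEN, so it does not describe Z1G. For the nearest match, the chance of no response at a true rate of 20% is 0.8^11 = 0.086 or 0.8^12 = 0.069. That is unremarkable.

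These rows assume that the 50% applies to the 25 expansion patients (Section 1.3 reports 48 solid-tumour patients in study 12871), that all 25 were assessed, and that the remaining PTEN-loss tumours were PIK3CA-unmutated. Section 1.4 also speaks of very few responses, which may mean more than one.

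**What if 20% did drive the design?** In 35 patients the expected responses are 35 × 0.20 = 7.0, 35 × 0.10 = 3.5 and 35 × 0.08 = 2.8. The chance of seven or more is 56.7%, 5.5% and 1.9%. Seven is simply 20% of 35; no such threshold appears in the document. With an assumed null rate of 5% and success at five or more responses (exact one-sided alpha 0.029), power is 85.7% at 20%, 61.9% at 15% and 26.9% at 10%. A design built on 20% would be sensitive to it, but the Protocol does not say that this one is. The 20% stands in background prose and the 35 in the Schema. The subprotocol is used with the Master Protocol, which is not shown.

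**The case for a change.** The strongest case for acting is that the text reports the PIK3CA mutation and never draws the consequence. Nothing else in Section 1.4 supplies a response in a patient shown to be eligible. The 20% is the only arm-specific effect figure in the subprotocol, so readers will carry it into the results. A sentence on the responder's eligibility and a stated basis for 20% would cost little.

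The factual part stands: she would not be eligible, and the population behind 20% is not given. The inferences are weaker.

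- The only wording shown for level 3 asks for a PTEN-loss solid tumour that responded; it does not ask for unmutated PIK3CA. To declare that she does not count would assert a rule whose definition is not in the document.
- The very-little-data remark concerns this agent, while the 20% is credited to a report that, by its title, spans a drug class. The two statements do not contradict each other.
- A substitute range such as 8% to 20% would be no better founded. Its lower end, 1/12 to 1/13, counts the same patient, or else (1/11 to 1/12) requires an unreported one.
- On prediction, Section 1.4 describes Z1F, Z1G and Z1H as complementary and speaks of a signal of activity. It claims no formal predictive test.

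**Conclusion.** No change follows. Hypothesis and eligibility agree with each other; only the supporting evidence comes partly from neighbouring populations. That is ordinary for a phase II arm looking for a signal, and the text is open about both the mutation and the thin data. On the closest counts available (0 of 11 or 12), the upper limits of 28.5% and 26.5% leave 20% neither excluded nor supported.

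The observed response proportion in 35 patients and its confidence interval do not depend on the rate that was anticipated. Noting the responder's ineligibility, naming the population behind 20% or rewording the hypothesis as estimation would annotate the introduction. None of these would alter eligibility, endpoint, sample size, analysis or conclusion.

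This rests on the assumptions given with the counts, and on the absence of any link in this document between 20% and the accrual goal or a decision rule.

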1.2 Copanlisib

Copanlisib (BAY 80-6946) is a novel, highly selective, pan-class phosphatidylinositol 3-kinase (PI3K) inhibitor with potent activity against both the δ and α isoforms. A summary of the available relevant non-clinical and clinical

data is provided below. Study details and additional information can be found in the Investigator Brochure.

1.2.1 Preclinical Data

The pharmacodynamic effects of copanlisib have been characterized extensively in preclinical cancer models, including cell lines and xenografts with loss of PTEN (see Investigator Brochure for detailed description of results). In enzymatic assays, copanlisib inhibited all PI3K isoforms with single digit nanomolar IC50, whereas no significant activity was seen against a panel of 220 other kinases, except mTOR (IC50 45 nM). Further testing supports a 100- to 1000-fold cellular selectivity for inhibition of PI3K versus mTOR signaling by copanlisib. Inhibition of both AKT activation and cell proliferation *in vitro* was achieved with copanlisib treatment in cancer cell lines of multiple types, including several with PTEN loss (Investigator Brochure, Table 4-4 and Figure 4-1, and Liu et al., 2013).¹⁵

In vivo preclinical testing also demonstrated efficacy in multiple cancer xenograft models. Notably, partial tumor regression was observed in the U87 glioblastoma model, which has loss of PTEN function due to an in-frame PTEN deletion that results in a truncated protein.⁹

1.2.2 Clinical Data

As of Feb 01, 2016, 627 patients with advanced cancer have been treated across eight phase 1, three phase 2 and three phase 3 studies. Copanlisib has also been studied in healthy volunteers

1.2.3 Pharmacodynamics:

The PD effects on glucose and plasma insulin levels as well as 18[F]FDG-CT/PET have been investigated in the first-in-man Study 12871 using copanlisib monotherapy at different doses. All but 1 of the 47 non-diabetic patients treated at 0.4 mg/kg copanlisib experienced a PD effect as well as all 6 diabetic patients treated at 0.4 mg/kg copanlisib. Peak plasma glucose values were seen 5 to 8 hours after the start of the copanlisib infusion. Hyperglycemia was reversible, i.e., not observed after copanlisib treatment had been permanently discontinued. Dose-related increases in glucose and insulin as well as copanlisib exposure-related increases in plasma glucose were observed. Plasma insulin increase to greater than 2 times the baseline value was reported in 90% of the patients, starting at the 0.2 mg/kg dose level. The PI3K pathway is required for downstream signaling from the insulin receptor. Inhibition of this pathway is expected to lead to impaired cellular uptake of glucose, with a subsequent reactive rise in plasma insulin and glucose levels. Paired FDG-PET scans were available in 21 patients. Between baseline and Cycle 1 Day 3 or Cycle 1 Day 4, 7 patients (33%) showed a reduction of more than 25% in FDG uptake. There was a weak correlation between changes in maximum standard uptake value (maximum standard uptake value [SUVmax]) and AUC(0-25) of copanlisib.

1.2.4 Pharmacokinetics:

Copanlisib (BAY 80-6946) PK have been characterized in the following studies in cancer patients: (i) single agent dose escalation study in cancer patients in the US (Study 12871), (ii) a dose escalation study in combination with refametinib (BAY 86-9766) in the US and Europe (Study 12876), (iii) a single agent dose escalation study in cancer patients in Japan (Study 15205), in two studies in combination with chemotherapy, either with paclitaxel (Study 12874), or with gemcitabine and gemcitabine/cisplatin (Study 12875). Furthermore, Study 16790 a PD study with copanlisib as monotherapy in patients with NHL and solid tumors as well as a Study 16270 to evaluate potential drug-drug interaction of copanlisib with itraconazole (a strong CYP3A4 inhibitor) and rifampin (a strong CYP3A4 inducer) are ongoing. Results on single agent studies is summarized below. Please refer to the IB for pharmacokinetics of copanlisib in combination with other drugs.

In Study 12871, copanlisib PK were characterized on Cycle 1 Day 1 and 15 and Cycle 3 Day 15. In general, PK data indicate similar copanlisib Cmax and AUC(0-25) on Day 1 and Day 15, indicating lack of significant accumulation after once weekly administration. Dose proportional increase in copanlisib exposure (Cmax and AUC(0-25)) was observed between 0.1 mg/kg to 1.2 mg/kg with moderate to high inter-subject variability. At the MTD of 0.8 mg/kg (n=28), the geometric mean copanlisib terminal phase t1/2 was 38.2 hours (CV: 42.5%), which supports once weekly dosing. No accumulation was observed after once weekly dosing when comparing PK on Cycle 1 Days 1 and 15 and Cycle 3 Day 15. No evidence of time-dependency in the PK of copanlisib was observed.

In Study 15205, copanlisib doses of 0.4 mg/kg and 0.8 mg/kg were evaluated in Japanese patients. Pharmacokinetic results at the 0.4 and 0.8 mg/kg dose level indicate generally comparable (slightly lower) exposure in Japanese patients and non-Japanese patients enrolled in the US Study 12871.

Study 16270 is an ongoing 2 armed Phase 1 study aims to evaluate the effect of itraconazole (a strong CYP3A4 inhibitor) or rifampin (a strong CYP3A4 inducer) on the PK of single i.v. doses of copanlisib and evaluates parameters of cardiac safety in patients with advanced solid tumors. Cycle duration is 4 weeks. Arm A evaluates the effect of itraconazole on copanlisib PK. Arm B evaluates the effect of rifampin on copanlisib PK and the effect of copanlisib on QTc and left ventricular ejection fraction (LVEF).

The PK of copanlisib were characterized after a 1 hour i.v. infusion administered once weekly. In the dose escalation cohorts, serial PK samples were collected on Cycle 1 Day 1 (up to 48 hours after end of infusion at dose levels \leq 0.2 mg/kg and approximately 168 hours after the start of infusion at dose levels $>$ 0.2 mg/kg) and Cycle 1 Day 15 (up to 24 hours after the end of infusion). In general, PK data indicate similar copanlisib Cmax and AUC(0-25) on Day 1 and Day 15, indicating lack of significant accumulation after once weekly

administration. Nearly dose proportional increase in copanlisib exposure (Cmax and AUC(0-25)) was observed between 0.1 mg/kg to 1.2 mg/kg with moderate to high inter-subject variability. In the MTD expansion cohort, serial PK samples were collected on Cycle 1 Day 1 and 15 and Cycle 3 Day 15 (up to 8 hours after the end of infusion). At the MTD of 0.8 mg/kg, Cycle 1 Day 1, geometric mean (n=41) Cmax was 454 μ g/L and AUC(0-tlast), exposure covering the 1-week dosing interval, was 2880 μ g•h/L. Inter-patient variability in copanlisib Cmax and AUC(0-tlast) at 0.8 mg/kg was high with values of 73.3% CV for Cmax and about 46.5% for AUC(0-tlast). The geometric mean copanlisib terminal phase t1/2 was 38.2 hours (CV: 42.5%), which supports once weekly dosing. Reliable terminal t1/2 could only be calculated in 28 patients. After administration of 0.4 mg/kg copanlisib to 6 diabetic patients, geometric mean Cmax was 138 μ g/L (CV: 36.7%) on Cycle 1 Day 1 and 151 μ g/L (CV: 23.4%) on Cycle 1 Day 15. Geometric mean AUC(0-25) was 607 μ g•h/L (CV: 43.6%) on Cycle 1 Day 1 and 687 μ g•h/L (CV: 36.0%) on Cycle 1 Day 15. Inter-subject variability for copanlisib Cmax and AUC(0-25) was moderate to high and similar to variability in other cohorts with PK parameters varying by a factor of about 3. Applying a adjusted body weight dosing, AUC(0-25) values on Cycle 1 Day 1 in obese patients were similar to AUC(0-25) values of other patients with normal BMI (130 mg/m²).

